5.2 Safety Variables

Safety is monitored in this study by collection of adverse events, vital signs, electrocardiography, C-SSRS, and clinical laboratory measures. It is noted that all untoward events or experiences are reported as adverse events regardless of whether they are identified by clinical observation, subject reporting, physical examination, clinical laboratory test result, electrocardiography, or any other examination or test. It is noted that listings are reviewed by medically qualified individuals including vital signs, laboratory data, electrocardiograms (ECG), and all safety data from all other sources to ensure that safety signals are identified and reported in the analysis of the safety data from this study.

5.2.1 Treatment-emergent Adverse Events

Adverse events will be coded using Medical Dictionary for Regulatory Activities (MedDRA) Version 16.0 or above. Adverse event coding will be done to the lowest level term (LLT). Adverse events will be summarized by System Organ Class (SOC) and preferred terms (PT).

Definitions:

- A treatment-emergent adverse event (TEAE) is an event that is observed or reported after administration of study medication that was not present prior to study medication administration or an event that represents the exacerbation of a pre-existing event.
- An adverse withdrawal is a subject who withdrew from the study due to an adverse event.
- A serious adverse event (SAE) is an AE that is classified as serious according to the criteria specified in the study protocol.

Safety and tolerability variables based on adverse events include the following:

- Proportions of subjects with TEAEs by Preferred Term and decreasing frequency of AEs

- Proportions of subjects with TEAEs by System Organ Class and Preferred Term
- Proportions of subjects with related TEAEs
- Proportions of subjects with severe TEAEs
- Proportions of subjects with treatment-emergent SAEs.
- Subjects with TEAEs that result in study termination

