6.4 SUBJECT WITHDRAWAL

Participants may withdraw from the study at any time at their own request or the request of their study partner, caregiver/informant/guardian, or they may be withdrawn at any time at the discretion of the Investigator or Sponsor for safety, behavioral, compliance, or administrative reasons. If a participant does not return for a scheduled visit, every effort should be made to contact the participant including certified letter, return receipt requested. The investigator should inquire about the reason for withdrawal, request that the participant return all unused investigational product(s), request that the participant return for any remaining clinic visits.

If the participant withdraws from the study and joins another clinical study or does not wish to complete the remaining clinic visits, an Early Termination and/or Follow-up Visit should be performed as follows:

- An Early Termination should be performed if less than 45 days have elapsed since the subject's last dose of study drug.
- A Follow-up Visit should be performed when \geq 45 days have elapsed since the subject's last dose of study drug.

Continued follow-up with the participant may be required if there are any unresolved adverse events (refer to Section 8.7).

If the participant withdraws from the study, and also withdraws consent for disclosure of future information, no further evaluations should be performed, and no additional data should be collected. The Sponsor may retain and continue to use any data collected before such withdrawal of consent. An individual patient enrolled in the trial may be discontinued from dosing (and continue in the study) based on a specific adverse event profile as recommended by either the IDMC and/or the Sponsor in discussions with the PI. The IDMC or the Sponsor may temporarily stop dosing of enrolled subjects and/or additional enrollment of new patients at any time and may permanently terminate the study at any time.

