Any emergent medical condition or safety finding that, in the opinion of the Investigator, may jeopardize the participant's safety if he/she continues dosing will be sufficient reason to discontinue dosing (temporarily or permanently), while the participant continues in the study. The participant should be followed as indicated for the AE until resolved, declared stable or the participant is lost to follow up. Safety data will be obtained from the physical and neurological examination, vital signs, routine laboratory tests, ECG, and neuropsychological testing batteries. Once resolved, the Investigator and Medical Monitor may discuss if it would be appropriate to re-start dosing.

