8.6 DOCUMENTATION OF ADVERSE EVENTS

The condition of each study subject will be monitored throughout the study. Signs and symptoms of possible AEs may be observed by the staff, elicited by asking an open or indirect question (e.g., “How have you been feeling?”) or volunteered by the subject. All AEs, whether observed by the Investigator or clinical site staff, elicited from the subject, or volunteered by the subject, will be recorded on the adverse event page(s) of the CRF. Data will include start and end dates, concomitant medications given for AE, Investigator-specified severity, relationship to study drug, and action taken. All AEs should be reported to the study Sponsor.

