9.8.1 Safety Variables of Analysis

9.8.1.1 Adverse Events

Definitions:

- A *treatment-emergent adverse event* (TEAE) is an event that is observed or reported after administration of study medication that was not present prior to study medication administration or an event that represents the exacerbation of a pre-existing event.
- An *adverse withdrawal* is a subject who withdrew from the study due to an adverse event.
- A *serious adverse event* (SAE) is an AE that is classified as serious according to the criteria specified in the study protocol.

Adverse events variables of analysis include:

- Proportions of subjects with TEAEs by Preferred Term and decreasing frequency of TEAE
- Proportions of subjects with TEAEs by System Organ Class and Preferred Term
- Proportions of subjects with adverse withdrawals

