9.8.2 Statistical Methodology for Safety Analysis

Adverse events will be coded using MedDRA Version 21.0 or above. Adverse event coding will be done to the lowest level term (LLT). All treated patients will be included in the assessment of safety. Adverse events will be summarized by MedDRA System Organ Class and Preferred Terms. Separate tabulations will be produced for related AEs (those considered by the Investigator as drug related), SAEs, discontinuations due to AEs, and severe events.

Vital signs, ECG results, and laboratory data will be tabulated for changes over time on study. In addition, TEAV and significant findings will be summarized.

For each post-Baseline assessment, descriptive statistics are provided for the assessment value and the change from Baseline to the assessment.

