1.9 Modifications from the Statistical Section of the Protocol

The power calculation was updated from the protocol and the composite score analysis was added. Secondary variables (MMSE and biomarkers) and exploratory assessment of ADAScog11 progression were added. In addition, the statistical analysis plan adds more detail and analyses and supersedes the statistical section of the protocol.

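### The SAP's only measure of discontinuation for adverse events is leaving the study, so patients who stop study drug for an adverse event but stay in the study are not identified

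*SAP*

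**What the plan says.** **SAP, Part 1.** Section 5.2.1 gives the definition: "An adverse withdrawal is a subject who withdrew from the study due to an adverse event". The list of AE variables that follows has six entries. The last, and the only one about discontinuation, is "Subjects with TEAEs that result in study termination". The disposition table in SAP 6.8 covers patients who withdrew before completing the study and their reasons. The supportive AE listing in SAP 6.9.1 names its fields, and action taken is not among them.

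**Protocol, conduct.** Section 6.4 separates stopping drug from leaving the study, in two places. On the recommendation of the data monitoring committee or the sponsor, in discussion with the investigator, a patient "may be discontinued from dosing (and continue in the study) based on a specific adverse event profile". And a condition or finding that the investigator thinks may endanger the participant if dosing goes on "will be sufficient reason to discontinue dosing (temporarily or permanently), while the participant continues in the study". That paragraph also provides for AE follow-up and a possible restart of dosing.

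**Protocol, analysis.** Section 9.8.1.1 uses the same study-level definition and lists "Proportions of subjects with adverse withdrawals". Section 9.8.2 asks for separate tabulations that include "SAEs, discontinuations due to AEs, and severe events", without saying whether drug or study is meant.

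**Which governs.** SAP 1.9 says that the SAP "supersedes the statistical section of the protocol". Protocol 9.0 says the same.

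**The concern.** Safety and tolerability over 6 months is a stated secondary objective of Part 1 (SAP 1.1), and how often an adverse event makes patients stop the drug is a direct measure of it. The protocol provides a route by which drug is stopped for safety and the patient is kept under observation. The SAP's discontinuation variable does not see anyone on that route.

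A reader of the study report would find a row for events ending study participation and could easily take it as the number of patients who could not tolerate the drug. With 43 patients enrolled (SAP 1.4), or 21 to 22 per arm, one or two patients can change that impression. Part 1 may also inform the dose and eligibility criteria of Part 2 (protocol 9.1), and protocol 9.8.1.1 carries the same definition into an 18-month study.

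**Working it through.** The documents state no discontinuation rate, so there is no figure to reproduce. The check is first textual and then a short illustration.

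**Step 1. Follow one patient through the outputs.** Suppose a patient permanently stops drug for an adverse event under protocol 6.4, attends the remaining visits and completes Month 6.

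| Output | Does it show that the event led to stopping drug? |
|---|---|
| SAP 5.2.1, TEAE, related, severe and serious-event variables | No. The event is counted wherever it qualifies, but not the drug stop |
| SAP 5.2.1, TEAEs ending study participation | No. The patient did not leave the study |
| SAP 6.8, disposition | No. Only study withdrawals and reasons are named |
| SAP 6.9.1, AE listing | No. Action taken is not a named field |
| SAP 4, per-protocol set | No. Taking under half the medication may exclude the patient, but the set is optional and is not a tolerability count |

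**Step 2. Is the information collected?** Protocol 8.6 says of the AE page: "Data will include start and end dates, concomitant medications given for AE, Investigator-specified severity, relationship to study drug, and action taken". The response options for action taken are not given. I assume that they distinguish permanent stop from interruption of study drug, and this should be confirmed on the eCRF.

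**Step 3. How much could be missed?** Let n be the patients per arm, p the true proportion who stop drug for an AE, and s the share of those who stay in the study. Assume that all who do not stay are recorded as leaving because of that event. Then:

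- all drug stops = n × p
- counted by the SAP variable = n × p × (1 − s)
- missed fraction = s

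Only n is documented: 43 / 2 = 21.5, taken as 22. The values of p and s are assumptions.

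| p | All drug stops, 22 × p | Counted, s = 25% | s = 50% | s = 75% | s = 100% |
|---|---|---|---|---|---|
| 5% | 1.10 | 0.83 | 0.55 | 0.28 | 0 |
| 10% | 2.20 | 1.65 | 1.10 | 0.55 | 0 |
| 20% | 4.40 | 3.30 | 2.20 | 1.10 | 0 |

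At s = 0 nothing is missed.

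**Step 4. The difference between arms.** If s is the same in both arms, the difference shrinks by the factor (1 − s). With assumed true rates of 20% and 10% and s = 50%, the counted rates are 20% × 0.5 = 10% and 10% × 0.5 = 5%, so 10 points become 5.

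If s differs between arms, the direction is open. With s = 25% on azeliragon and 75% on placebo, the same true rates are counted as 20% × 0.75 = 15% and 10% × 0.25 = 2.5%. The difference is then 12.5 points, larger than the true 10.

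**The case against.** The strongest reply is that the SAP variable is correctly labelled. Counted as written, it gives the number of patients whose events ended study participation, and the SAP does not present it as a drug-stop rate. That stands: a second, different count is missing, and the first is not wrong.

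Four stronger readings might be inferred, and the documents do not support them.

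- *The tolerability endpoint is biased.* There is no such single endpoint. This is one of six AE variables, and protocol 2.2.1 lists adverse events generally as a safety endpoint.
- *These patients drop out of the safety reporting.* They remain in the safety set and their events are tabulated. Only the link between event and drug stop is lost.
- *The protocol directs sites to stop drug and keep the patient.* Section 6.4 says that dosing may be stopped, or that there is sufficient reason to stop it. It equally allows withdrawal from the study for safety reasons. The share who stay could be zero.
- *The shortfall is larger in the arm with more toxicity.* That needs a similar staying share in both arms, which nothing in the documents supports.

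It can also be said that protocol 9.8.2 already covers drug stops, and that SAP 1.9 does not list dropping that tabulation among its changes. This has some force, especially for Part 2, since this SAP covers Part 1 only. For Part 1 it does not settle the matter. The protocol term is undefined, the SAP's list states the item as study termination, and the SAP takes precedence. A programmer working from the SAP would build the narrower table.

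Finally, the SAP allows exploratory and data-driven displays (section 10), and the field is on the AE page, so the count could be recovered later. That lowers the severity, but a planned row is better than one added after the data are seen.

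**Conclusion.** The point holds as a gap in safety reporting. SAP 5.2.1 measures AE-related discontinuation only as leaving the study, protocol 6.4 allows stopping drug without leaving, and no specified SAP output identifies the patients in between.

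The size cannot be derived from the documents. The missed fraction equals the share who stop drug for an adverse event and stay, from 0% to 100%. Under the assumed rates of 5% to 20%, that is at most about 1 to 4 patients per arm. Neither the size nor the direction of any effect on the comparison between arms can be stated without assuming that share in each arm.

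Severity: should be fixed. The safety analysis is descriptive, and no hypothesis test, alpha, power figure or efficacy result depends on this row.

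**What to change.** In the Part 1 SAP, before unblinding:

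- **5.2.1 and 6.9.1:** add subjects with TEAEs leading to permanent discontinuation of study drug and, as a separate row, to temporary interruption. Take both from the action-taken field, whether or not the patient stays in the study.
- **5.2.1:** keep TEAEs leading to study withdrawal as its own row, labelled as such.
- **6.8:** add treatment discontinuation, with reasons, to the disposition table beside study withdrawal.
- **6.9.1:** add action taken to the AE listing.

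For Part 2, state in protocol 9.8.2 that discontinuations due to AEs means discontinuation of study drug, and align the definition and variable in 9.8.1.1.

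The cost is some wording and a few extra descriptive rows. If the action-taken options are as assumed, no new data are needed. The change concerns reporting only and leaves the rules for stopping or restarting dosing as they are.

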5.2.2 The Columbia Suicide Severity Rating Scale (C-SSRS)

- **Range:** The following outcomes are C-SSRS categories and have binary responses (yes/no). The categories have been re-ordered from the actual scale to facilitate the definitions of the composite and comparative endpoints, and to enable clarity in the presentation of the results.
 - Category 1 – Wish to be Dead
 - Category 2 – Non-specific Active Suicidal Thoughts
 - Category 3 – Active Suicidal Ideation with Any Methods (Not Plan) without Intent to Act
 - Category 4 – Active Suicidal Ideation with Some Intent to Act, without Specific Plan
 - Category 5 – Active Suicidal Ideation with Specific Plan and Intent
 - Category 6 – Preparatory Acts or Behavior
 - Category 7 – Aborted Attempt
 - Category 8 – Interrupted Attempt
 - Category 9 – Actual Attempt (non-fatal)
 - Category 10 – Completed Suicide

Self-injurious behavior without suicidal intent is also a C-SSRS outcome (although not suicide-related) and has a binary response (yes/no).

The following outcome is a numerical score derived from the C-SSRS categories. The score is created at each assessment for each patient and is used for determining treatment emergence.

Suicidal Ideation Score: The maximum suicidal ideation category (1-5 on the C-SSRS) present at the assessment. Assign a score of 0 if no ideation is present.

Endpoints:

Composite endpoints based on the above categories are defined below.

- **Suicidal ideation:** A “yes” answer at any time during treatment to any one of the five suicidal ideation questions (Categories 1-5) on the C-SSRS.
- **Suicidal behavior:** A “yes” answer at any time during treatment to any one of the five suicidal behavior questions (Categories 6-10) on the C-SSRS.
- **Suicidal ideation or behavior:** A “yes” answer at any time during treatment to any one of the ten suicidal ideation and behavior questions (Categories 1-10) on the C-SSRS.

Comparative endpoints of interest are defined below. “Treatment emergence” is used for outcomes that include events that first emerge or worsen. “Emergence” is used for outcomes that include events that first emerge.

- Brief description: The Columbia Suicide Severity Rating Scale (C-SSRS) is a joint interview with the caregiver and patient that systemically assesses suicidal ideation and suicidal behavior (Posner et al, 2007). This scale will be administered at Screening Visit to evaluate lifetime suicide attempt, suicide behaviors, and other non-suicidal self-injuries. Positive responses on the C-SSRS will be mapped to the Columbia Classification Algorithm of Suicide Assessment (C-CASA) for classification and reporting using a standard algorithm.)

5.2.3 Vital Signs

Vital signs measurements consist of blood pressure and pulse rate. Variables of analysis will include means, mean changes over time, and proportions of subjects meeting criteria for potential clinical concern in vital signs:

- Mean and mean changes in systolic and diastolic blood pressures
- Mean and mean changes in pulse
- Proportions of subjects with treatment-emergent values or changes of potential clinical concern.

5.2.4 ECG

12-lead ECGs are obtained at the Screening, Baseline, Month 3, Month 6/ET, and Follow-up visits. Triplicate measurements are obtained at Baseline; all other study visits collect single measurements.

ECG results will be obtained from the Central Reader. Interpretation of results as normal, abnormal not clinically significant or abnormal clinically significant will also be collected from the investigator or designee.

5.2.5 Clinical laboratory assessments

Routine clinical laboratory data, including eGFR, will be summarized with descriptive statistics on assessment values and change from Baseline. Routine clinical laboratory data will also be evaluated on the basis of laboratory-defined reference ranges and clinically important values or changes, as defined in this document (Section 10). Routinely collected laboratory safety data that are not required by the protocol will be considered source data, and will not be captured for inclusion into the study database.

Definition:

- A treatment-emergent abnormal value (TEAV) is a laboratory value that is abnormal after administration of study medication that was normal prior to study medication administration.

- A TEAV of potential clinical concern is a value or change that meets criteria specified in this SAP in Section 10.

Laboratory analytes in this study include:

- Hematology
 - Hemoglobin
 - Hematocrit
 - Erythrocyte (RBC) count
 - Platelet count
 - Total leukocyte (WBC) count
 - MCV
 - Leukocyte differential (percent and total)
 - Total neutrophils
 - Eosinophils
 - Monocytes
 - Basophils
 - Lymphocytes
- Clinical chemistry
 - BUN
 - Creatinine
 - Glucose
 - HbA1c
 - Calcium
 - Sodium
 - Potassium
 - Chloride
 - Bicarbonate
 - AST
 - ALT
 - GGT
 - LDH
 - Total bilirubin
 - Alkaline phosphatase
 - Uric acid
 - Albumin
 - Total protein
 - Phosphorus

Safety variables of analysis include:

- Subjects with TEAVs
- Subjects with TEAVs of potential clinical concern (based on criteria in this SAP)
- Subjects with a TEAV in a liver function test (LFT)

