2.2 ENDPOINTS

2.2.1 Part 1

Primary Endpoint:

- Change from Baseline in the ADAS-cog14 at Month 6

Secondary Endpoints:

- Change from Baseline in the CDR-sb at Month 6
- Change from Baseline in the FAQ at Month 6
- Change from Baseline in the Amsterdam-IADL at Month 6
- Change from Baseline in eGFR at Month 6

Safety Endpoints:

- Adverse events, clinical laboratory tests, vital signs, 12-lead ECG, C-SSRS

2.2.2 Part 2

Co-Primary Endpoints:

- Change from Baseline in the ADAS-cog14 at Month 18
- Change from Baseline in CDR-sb at Month 18

Secondary Endpoints:

- Responder status at Months 6, 12, and 18 based on the ADAS-cog14
- Change from Baseline in FAQ score at Month 18
- Change from Baseline in Amsterdam-IADL score at Month 18
- Change from Baseline in MMSE score at Month 18
- Change from Baseline in eGFR at Month 18
- Change from Baseline in whole brain volume at Month 18

Safety Endpoints:

Adverse events, clinical safety laboratory tests, ECG, vital signs, C-SSRS

Exploratory Endpoints:

- Change from Baseline at Month 18 for measures of behavior and quality of life (NPI, DEMQOL-proxy)
- Change from Baseline at Months 3, 6, and 12 for the primary and secondary measurements: ADAS-cog14, FAQ, Amsterdam-IADL, CDR-sb, MMSE, NPI, DEMQOL-proxy
- Change from Baseline in plasma concentrations of A β species at Month 18
- Change from Baseline in brain MRI (hippocampal, ventricular) volumetric measures at Month 18

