9.7.1.2 Secondary Variables of Analysis

Part 1 secondary variables of analysis will include.

- Mean change from baseline in CDR-sb at Month 6.
- Mean change from baseline in the FAQ at Month 6.
- Mean change from baseline in the Amsterdam-IADL at Month 6.
- Mean change from baseline in eGFR at Month 6.

Part 2 will include the following secondary variables of analysis:

- Time to decline (to support responder analysis) where the specification of decline will be included in the SAP.

- Mean change from baseline in FAQ score at Month 18
- Mean change from baseline in Amsterdam-IADL score at Month 18
- Mean change from baseline in MMSE score at Month 18
- Mean change from baseline in eGFR at Month 18.
- Mean change from baseline in whole brain volume at Month 18.

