9.7.3 Statistical Methodology for Secondary and Other Efficacy Analysis

Secondary and exploratory endpoints that are measurement variables will use similar statistical methodology to the methodology used for primary analysis. Efficacy variables that are proportions will be analyzed using Mantel-Haenszel test. For the analysis of the categories for responders, a Cochran-Mantel-Haenszel test will be used.

Methodologies for variables that are proportions will include construction of confidence intervals for each treatment group and for the difference between groups. For analysis, Fisher's exact test will be used for single-population analysis, and a Mantel-Haenszel test will be used for analyses combining data across strata.

Methodologies for time-to-event variables will include construction of 95% confidence intervals for each group separately and for the difference between groups. For analysis, a Wilcoxon test will be used for single-population analysis, and a van Elteren test will be used for analyses combining data across strata.

Subgroup analyses will be done as identified in the SAP.

Responders based on the ADAS-cog14 total score will be described using Kaplan-Meier curves using the specification of responder (lack of decline) provided in the SAP. Also, a graphical representation will be defined where the y-axis will show the cumulative percentage of patients who achieved the specific measure of improvement in the ADAS-cog14 total score shown on the x-axis with a separate cumulative percentage curve for each treatment group.

If the distribution of any of the above parameters, key secondary, or other secondary endpoints does not appear to be normally distributed, the rank analogues will be advanced.

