1.1 Study Objectives

The primary objective of this study is:

- To evaluate the impact of 6 months of treatment with oral azeliragon on cognitive performance

The secondary objectives of this study are:

- To evaluate the efficacy of azeliragon treatment on measures of function and activities of daily living
- To evaluate the efficacy of azeliragon treatment on complications of diabetes
- To evaluate the safety and tolerability of 6 months of azeliragon treatment
- To evaluate the effect of azeliragon treatment on biomarkers and markers of inflammation

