5.1.2 Secondary Variables of Analysis

- Mean change from baseline in the Amsterdam-IADL at Month 6.
- Mean change from baseline in CDR-sb at Month 6.
- Mean change from baseline in the FAQ at Month 6.
- Mean change from baseline in the MMSE at Month 6.
- Mean change of treatment on biomarkers and markers of inflammation

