5.4 Adverse Events of Special Interest

Adverse events related to signs and symptoms of AD potentially pertain to efficacy as well as safety of the compound. Descriptive analysis will include TEAEs classified by MedDRA into the SOC for psychiatric disorders (at the SOC level within the hierarchy of MedDRA) and high level group terms (HLGTs) of anxiety disorders and symptoms (at the HLGT level within the hierarchy of MedDRA).

Standardized MedDRA queries (SMQs) will be used for dynamic analysis of any TEAE that emerges of potential interest.

Conditions associated with substance abuse are included in the SOC Psychiatric Disorders in high level term (HLT) “Substance-related disorders,” which will be used for identification of terms pertaining to substance abuse. Variables of interest will include incidence estimates for each treatment group for the HLT and PTs within the HLT. It is noted that terms that refer to a person as a “drug abuser” would be captured in the SOC Social Circumstances, which is not intended for contributing to variables of analysis.

6 Statistical Methodology

General statistical methods will be applied as appropriate for out-patient clinical studies. Safety evaluations will rely on descriptive statistics. Randomization groups will be examined for homogeneity between treatment groups.

Continuous variables will be summarized using mean, median, standard deviation, minimum, maximum, and number of subjects available for analysis. Categorical variables will be summarized using frequency, proportion, and number of subjects available for analysis.

SAS version 9.3 or later will be used.

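### The SAP moves Month 6 eGFR change from Part 1 secondary efficacy endpoint to descriptive safety laboratory data without declaring it, so no between-arm estimate is planned

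*SAP*

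**What the plan says.** Protocol 2.2.1 gives Part 1 four secondary endpoints: CDR-sb, FAQ, Amsterdam-IADL and "Change from Baseline in eGFR at Month 6". Protocol 9.7.1.2 repeats the last of these as a secondary variable of analysis, "Mean change from baseline in eGFR at Month 6". On method, Protocol 9.7.3 says "Secondary and exploratory endpoints that are measurement variables will use similar statistical methodology to the methodology used for primary analysis".

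SAP 1.1 still carries the secondary objective "To evaluate the efficacy of azeliragon treatment on complications of diabetes". The SAP's own secondary list (5.1.2) contains Amsterdam-IADL, CDR-sb, FAQ, MMSE and "Mean change of treatment on biomarkers and markers of inflammation", but not eGFR. The SAP names eGFR only in 5.2.5, under safety: "Routine clinical laboratory data, including eGFR, will be summarized with descriptive statistics on assessment values and change from Baseline". The opening of SAP Section 6 adds "Safety evaluations will rely on descriptive statistics".

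SAP 1.9 sets out the differences from the protocol. It reports a new power calculation and a composite score analysis, and then "Secondary variables (MMSE and biomarkers) and exploratory assessment of ADAScog11 progression were added". It says nothing about eGFR and ends by giving the SAP precedence over the protocol's statistical section.

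**The concern.** A pre-specified efficacy endpoint has changed category between protocol and SAP, and the section that exists to record such changes does not record it. The change has practical effects:

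- No treatment contrast is planned for eGFR.
- The analysis set moves from the FAS to the safety set (SAP Section 4).
- Baseline becomes the latest valid pre-dose value. For efficacy outcomes it is the average of screening and baseline (SAP 8.1).

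The retained objective asks about efficacy on diabetes complications. A study report that follows the SAP would have no planned effect estimate to offer on it. Because the SAP takes precedence, the protocol's method for secondary endpoints cannot be relied on to fill the gap. SAP 8.8 promises to document departures from the SAP itself, which would not catch this one.

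**Working it through.** The point rests on comparing the texts.

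| Question | Protocol | SAP |
|---|---|---|
| Objective on diabetes complications | Yes (2.1.1) | Yes (1.1) |
| eGFR among secondary endpoints or variables | Yes (2.2.1, 9.7.1.2) | No (5.1.2) |
| eGFR as exploratory or proof-of-concept variable | Not applicable | No (5.1.3, 5.1.4) |
| eGFR in the hypothesis sequence | No (9.4) | No (Section 2) |
| Method that reaches eGFR | Similar to the primary analysis (9.7.3) | Descriptive only (5.2.5, Section 6) |
| Change declared | – | No (1.9) |

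**Could another SAP section supply the comparison?**

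1. SAP 6.7 applies primary-type methods to secondary and exploratory endpoints. It can only refer to the SAP's own lists, and eGFR is on neither.
2. SAP 6.11 specifies a repeated-measures model with a treatment term, but for plasma inflammatory biomarkers only.
3. SAP 6.9.4, on laboratory data, gives mean, median, standard deviation, minimum and maximum at each assessment. Its reference to treatment groups concerns proportions with values of potential clinical concern. The criteria in SAP Section 11 have no eGFR entry.

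None of these yields a between-arm estimate for eGFR.

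**Does eGFR belong to the objective?** The documents do not map objectives to endpoints, so this is an inference. Protocol 1.1.1 and 1.1.3 name nephropathy as a complication of diabetes, which makes a renal measure a natural fit. The other three protocol secondary endpoints measure dementia severity or daily function.

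**Are the data available?** Protocol Table 1 schedules fasting central laboratory samples at Screening, Baseline, Month 3, Month 6 and Follow-up. Protocol 7.1.6.1 includes the eGFR calculation in the chemistry panel.

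**What precision could be expected?** The documents give no standard deviation or expected effect for eGFR, so power cannot be computed. Precision can be stated in SD units. SAP 1.4 gives 43 enrolled. For a simple two-group comparison:

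half-width = t(0.975, n1 + n2 − 2) × SD × √(1/n1 + 1/n2)

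- Assumed split 21/22, no missing data: 2.0195 × √(1/21 + 1/22) = 2.0195 × 0.3051 = 0.62 SD.
- Assumed 18% loss (the protocol's planning figure): 43 × 0.82 ≈ 35, split 17/18, giving 2.0345 × √(1/17 + 1/18) = 2.0345 × 0.3382 = 0.69 SD.

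Adjusting for baseline eGFR could narrow either interval.

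**The case against.** The best counter-argument is that the protocol may never have promised a Part 1 comparison. Protocol 9.7 reserves separate analysis by stage for ADAS-cog14 and CDR-sb and assigns inference on the other secondary variables to the study as a whole. This SAP covers Part 1 only. But Protocol 9.0 says the clinical efficacy variables are analysed separately for each study, and the SAP itself tests FAQ and Amsterdam-IADL in Part 1. The protocol is therefore inconsistent, and a firm promise of a Part 1 eGFR test cannot be read from it. That limits the point but does not explain why eGFR alone among the four protocol endpoints left the secondary list.

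It is also fair to say that little hangs on the result. eGFR was in neither testing sequence, so no alpha-controlled claim is lost. The stated uses of Part 1 are the effect on ADAS-cog14, the choice of functional co-primary and the Part 2 sample size, and none of them depends on eGFR. Precision at 43 subjects is poor. All of this stands. It argues for an estimate with an interval and no formal claim. It does not argue for leaving the estimate out, since the SAP models the other three protocol secondary endpoints at the same sample size.

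A reader might go further and infer that the diabetes-complications objective cannot be answered at all. The documents do not support that. Descriptive values and changes in eGFR are planned. If they are tabulated by arm, which 6.9.4 does not state for continuous measures, a reader could form an unadjusted difference. Nor is this the only objective without inference, because safety and tolerability is also handled descriptively. It would also be wrong to say that eGFR has vanished, since 5.2.5 names it openly. What is missing is the declaration in 1.9.

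**Conclusion.** The point holds as an undeclared reclassification. One of the protocol's four Part 1 secondary endpoints is now descriptive safety data, with no planned treatment difference, confidence interval or test, while the objective it most plausibly serves is kept. The conclusion assumes that SAP 6.7 refers to the SAP's own endpoint lists and that eGFR is the intended measure for that objective. The second assumption is an inference, though no other listed protocol secondary endpoint fits. The conclusion does not depend on settling whether the protocol intended inference by part or for the whole study. The primary analysis and the error control of the testing sequence are unaffected. The change should be made, but the trial's main conclusion does not turn on it.

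**What to change.** Restore "Mean change from baseline in eGFR at Month 6" to SAP 5.1.2. Analyse it with a repeated-measures model of the kind already in SAP 6.11, with terms for baseline eGFR, treatment, time and treatment-by-time. Report the Month 6 between-arm difference with its 95% confidence interval as a descriptive estimate outside the testing hierarchy. State which analysis set and which baseline definition apply, since the SAP's efficacy and safety rules differ on both. The 6.11 form suits this measure better than the primary model in SAP 6.2, whose risk score includes baseline MMSE.

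Also record in SAP 1.9 how the conflict between Protocol 9.0 and 9.7 on inference for secondary variables is resolved for Part 1.

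If the move to safety data was intended, declare and justify it in SAP 1.9 and align the objective in SAP 1.1 with what will be reported.

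The cost is a few lines of SAP text and one extra model. No new data collection is needed and no alpha is spent. The small downside is that the interval will be wide at 43 subjects and should be presented as such.
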